7.6.8. MUGA/Echocardiogram

LVEF abnormalities are defined according to CTCAE grade version 4.03. Participants will be considered as having a LVEF abnormality if the worst post value is grade 2, 3 or 4 according to the following classification:

- Grade 0: Non-missing value below Grade 2
- Grade 2: LVEF between 40% and 50%, inclusive, or absolute change from baseline between -10% and < -20%
- Grade 3: LVEF between 20% and 39%, inclusive, or absolute change from baseline \leq -20%
- Grade 4: LVEF lower than 20%.

A table reporting the worst post-baseline LVEF value using CTCAE grades will be produced. Different modalities to assess LVEF might be used for the same participant. The CTCAE grades will be provided regardless of the modality.

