- Left ventricular dysfunction: Symptomatic or asymptomatic decreases in ejection fraction occurred in 7% of patients, with Grade 3 left ventricular dysfunction occurring in 1.6% of patients.
- Hemorrhage: Hemorrhage occurred in 19% of patients, with events ≥ Grade 3 occurring in 3.2% of patients. Fatal intracranial hemorrhage in the setting of new or progressive brain metastases occurred in 1.6% of patients. The most frequent hemorrhagic events were gastrointestinal, including rectal hemorrhage (4.2%), hematochezia (3.1%), and hemorrhoidal hemorrhage (1%).
- Venous thromboembolism: Occurred in 6% of patients, including 3.1% of patients who developed pulmonary embolism.
- **Ocular toxicities:** Serous retinopathy is a class effect of MEK inhibitors. It is generally asymptomatic or mildly symptomatic and reversible (Urner-Bloch et al, 2016). Serous retinopathy occurred in 20% of patients. Symptomatic serous retinopathy occurred in 8% of patients with no cases of blindness. The median time to onset of the first event of serous retinopathy (all grades) was 1.2 months. RVO is a known class-related adverse reaction of MEK inhibitors and may occur in patients treated with binimetinib in combination with encorafenib. In patients with *BRAF* mutation-positive melanoma across multiple clinical trials, 0.1% of patients experienced RVO.
- **Pneumonitis/Interstitial Lung Disease**: Pneumonitis occurred in 0.3% of patients with *BRAF* mutation-positive melanoma across multiple clinical trials.
- **Hepatotoxicity:** The incidence of Grade 3 or 4 increases in liver function laboratory tests was 6% for ALT, 2.6% for AST and 0.5% for alkaline phosphatase. No patient experienced Grade 3 or 4 serum bilirubin elevation.
- **CK Elevation/Rhabdomyolysis**: Asymptomatic elevations of laboratory values of serum CK occurred in 58% of patients. Rhabdomyolysis was reported in 0.1% of patients with *BRAF* mutation-positive melanoma across multiple clinical trials.

- **QTc Prolongation:** QT prolongation has been observed in patients treated with BRAF inhibitors. Encorafenib is associated with dose-dependent QTc interval prolongation in some patients. In the COLUMBUS study, an increase in QTcF to > 500 ms was measured in 0.5% of patients.
- **Embryo-Fetal Toxicity:** Encorafenib or binimetinib can cause fetal harm when administered to pregnant women.

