- 6. Patient has not recovered to ≤ Grade 1 from toxic effects of prior therapy and/or complications from prior surgical intervention before starting study treatment. *Note:* Stable chronic conditions (≤ Grade 2) that are not expected to resolve (e.g., neuropathy, myalgia, alopecia and prior therapy-related endocrinopathies) are exceptions.
- 7. Current use of a prohibited medication (including herbal medications, supplements or foods), as described in Section 6.5.2, or use of a prohibited medication ≤ 1 week prior to the start of study treatment.
- 8. Impairment of gastrointestinal function or disease which may significantly alter the absorption of oral study treatment (e.g., uncontrolled nausea, vomiting or diarrhea, malabsorption syndrome, small bowel resection).
- 9. Impaired cardiovascular function or clinically significant cardiovascular diseases, including any of the following:
 - a. History of acute myocardial infarction, acute coronary syndromes (including unstable angina, coronary artery bypass graft, coronary angioplasty or stenting)
 ≤ 6 months prior to start of study treatment;
 - b. Congestive heart failure requiring treatment (New York Heart Association Grade ≥ 2);
 - c. LVEF < 50% as determined by MUGA or ECHO;
 - d. Uncontrolled hypertension defined as persistent systolic blood pressure ≥ 150 mmHg or diastolic blood pressure ≥ 100 mmHg despite optimal therapy;
 - e. History or presence of clinically significant cardiac arrhythmias (including uncontrolled atrial fibrillation or uncontrolled paroxysmal supraventricular tachycardia);
 - f. Triplicate average baseline QTcF interval ≥ 480 ms or a history of prolonged QT syndrome.

History of thromboembolic or cerebrovascular events ≤ 12 weeks prior to the first dose of study treatment. Examples include transient ischemic attacks, cerebrovascular accidents, hemodynamically significant (i.e. massive or sub-massive) deep vein thrombosis or pulmonary emboli.
 Note for all countries except Korea: Patients with either deep vein thrombosis or

Note for all countries except Korea: Patients with either deep vein thrombosis or pulmonary emboli that do not result in hemodynamic instability are allowed to enroll if they are stable, asymptomatic and on stable anticoagulants for at least 2 weeks. *Note:* Patients with thromboembolic events related to indwelling catheters or other procedures may be enrolled.

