| - | 15.00 | 2.00 | -1.18 | 16 | 300 | 90.0 | 0.07 | 0 | 210.0 | 525.0 | - | - | 6.0 |
| 12 | 16.00 | 1.88 | -1.20 | 15 | 320 | 96.0 | 0.06 | 0 | 224.0 | 560.0 | - | - | 6.4 |
| 13 | 20.00 | 1.50 | -1.30 | 10 | 400 | 120.0 | 0.05 | 0 | 280.0 | 700.0 | - | - | 8.0 |
| 16 | 40.00 | 0.75 | -1.60 | 5 | 800 | 240.0 | 0.03 | 0 | 560.0 | 1400.0 | - | - | 16.0 |
| 20 | 100.00 | 0.30 | -2.00 | 0 | 2000" | 600.0 | 0.01 | 0 | 1400.0 | 3500.0 | - | - | 40.0 |
| 30 | 1000.00 | 0.03 | -3.00 | 0 | 200001 | 6000.0 | 0.001 | 0 | 14000.0 | 35000.0 | - | - | 400.0 |

Bold values are standard logMAR progression.

LogMAR = logarithm of the minimum angle of resolution

*20/2000 is equivalent to counting fingers @ 2 feet

120/20000 is equivalent to hand motion @ 2 feet

Holladay J. Visual acuity measurements. J Cataract Refract Surg. 2004;30(2) 297-90.

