
 • To evaluate the safety and tolerability of encorafenib + binimetinib in treatment-naïve and previously treated participants with BRAF^{V600E}-mutant NSCLC 	
 • Incidence and severity of AEs graded according to the NCI CTCAE v4.03 and changes in clinical laboratory parameters, vital signs, ECGs and ECHO/MUGA scans
Exploratory Objectives	Exploratory Endpoints

 • To evaluate the PK of encorafenib, its metabolite LHY746, and binimetinib in participants with BRAF^{V600E}-mutant NSCLC 	
 • Plasma concentration-time profiles and PK parameter estimates for encorafenib, its metabolite LHY746, and binimetinib

 • To assess blood ctDNA mutation status 	
 • Genomic analysis of ctDNA in blood samples

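### SAP 7.6.8: the upper bound of the LVEF Grade 2 change band is reversed, so coded as written a fall of 10 to <20 points ending above 50% is tabulated as Grade 0

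*SAP*

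**What the plan says.** SAP 7.6.8 (MUGA/Echocardiogram) opens with "LVEF abnormalities are defined according to CTCAE grade version 4.03" and then sets out its own classification, on which the tabulation is to be based:

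- Grade 0: "Grade 0: Non-missing value below Grade 2". No Grade 1 is defined, so this is the residual category.
- Grade 2: LVEF from 40% to 50% inclusive, "or absolute change from baseline between -10% and < -20" percent.
- Grade 3: "Grade 3: LVEF between 20% and 39%, inclusive, or absolute change from baseline" of -20% or lower.
- Grade 4: LVEF below 20%.

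A participant counts as having an LVEF abnormality only if the worst post-baseline grade is 2, 3 or 4. The one output the section specifies is a table of worst post-baseline grade. No other section of the SAP or protocol restates the Grade 2 change band.

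The table serves a named secondary safety endpoint: SAP 3.1 lists "changes in clinical laboratory parameters, vital signs, ECGs and ECHO/MUGA scans". Protocol 5.2 excludes patients with "LVEF < 50% as determined by MUGA or ECHO", so eligible baselines start at 50%.

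**The concern.** Changes from baseline are written here as signed numbers, with a fall negative. The Grade 3 line uses that sign convention correctly. The Grade 2 line does not: its second bound points toward larger falls, into Grade 3 territory, when it should stop short of -20. Taken at face value, the change criterion for Grade 2 does no work.

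The level criterion hides much of this, because a moderate fall that lands at 40% to 50% is still Grade 2. What remains exposed is a moderate fall from a high baseline that stays above 50%. Such a participant would drop into the residual Grade 0 and out of the count of LVEF abnormalities. At stake is the completeness of the only LVEF table that SAP 7.6.8 specifies.

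**Working it through.** **Inputs.** The grading rules are those of SAP 7.6.8. The baseline floor of 50% comes from Protocol 5.2. Two assumptions are mine: the highest qualifying grade takes precedence, and LVEF is a whole number. An upper limit for baseline is also needed for counting; no document gives one, so it is varied below.

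**Notation.** C = post-baseline LVEF minus baseline LVEF, in percentage points.

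**Step 1: what the clause selects.** The documents give no worked figure to reproduce, so the clause is coded each way it can be read.

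- Literal, with -10 as the lower limit: C ≥ -10 and C < -20. No value satisfies both, so the set is empty.
- Literal, with -10 as the upper limit: C ≤ -10 and C < -20. This reduces to C < -20, which lies wholly inside Grade 3 (C ≤ -20).
- Size of fall, 10 to <20 points: -20 < C ≤ -10. In whole points this is -19 to -10, and it meets Grade 3 with no gap or overlap.

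Under either literal coding, nobody reaches Grade 2 by change alone.

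**Step 2: which falls are affected.** A fall of at least 10 points that ends above 50% needs a baseline above 60%. Examples:

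| Baseline to post | C | Literal | Size of fall |
|---|---|---|---|
| 61% to 51% | -10 | Grade 0 | Grade 2 |
| 68% to 53% | -15 | Grade 0 | Grade 2 |
| 72% to 53% | -19 | Grade 0 | Grade 2 |
| 65% to 50% | -15 | Grade 2 (by level) | Grade 2 |
| 72% to 52% | -20 | Grade 3 | Grade 3 |

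**Step 3: extent on a grid.** For baseline B, the number of the ten whole-point falls (10 to 19) that end above 50% is max(0, min(10, B - 60)). That gives 0 for B = 50 to 60, 1 at 61, 5 at 65, 8 at 68, and 10 from 70 upward.

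- Baselines 50 to 80: 31 × 10 = 310 combinations. Affected: 45 (B = 61 to 69) + 11 × 10 (B = 70 to 80) = 155, or 50%. Of the other 155, 110 end at 40% to 50% and stay Grade 2, and 45 end below 40% and are Grade 3.
- Baselines 50 to 75: (45 + 6 × 10)/260 = 105/260 = 40%.
- Baselines 50 to 70: (45 + 10)/210 = 55/210 = 26%.

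Across all 2,201 whole-number pairs of baseline 50 to 80 and post-baseline 10 to 80, correcting the bound moves exactly those 155 from Grade 0 to Grade 2 and changes no other pair.

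**Step 4: non-integer values.** The level bands stop at 39% and restart at 40%. A value of 39.5% therefore has no level-based grade. From a baseline of 55% (C = -15.5) it would be Grade 0 under literal coding and Grade 2 by change under the size-of-fall band. The documents do not state the precision with which LVEF is recorded, so this may never arise.

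**The case against.** The strongest reply is that nobody would program the literal clause. The Grade 3 line is the exact complement of a band from 10 to <20. The section invokes CTCAE v4.03. The SAP elsewhere uses a less-than sign simply to mark the excluded end of a range, as in the time-to-response intervals of 7.5.3 and the LogMAR change categories of 7.6.9. A clause that can never assign a grade should also be caught by the validation described in SAP Section 8. This largely stands: the intended band is clear, and read that way the clause misgrades nobody.

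It does not dispose of the point. The size-of-fall reading means ignoring the minus sign in the Grade 2 line and honouring it in the Grade 3 line; ignoring it in both would make Grade 3 a fall of 20 points or less. The section also bases grading on its own listed classification, and that list contains the faulty bound.

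A reader might infer that about half of all moderate LVEF falls would go unreported. The documents do not support that. The 50% share is a proportion of equally weighted possible values and depends on an assumed baseline ceiling of 80%. It falls to 40% or 26% with a ceiling of 75% or 70%, and no distribution of LVEF is given.

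A reader might also infer that cardiac toxicity would be hidden or patient care altered. That is not supported either. Events that investigators report as adverse events still enter the AE and AESI tables, and dose modification follows Protocol Appendix 3, not these SAP grades. The AE tables are only a partial check, though: under Protocol Appendix 4 an abnormal safety assessment counts as an AE on the investigator's judgment of clinical significance, with mandatory recording rules only for laboratory results. An asymptomatic fall that stays above 50% need not appear there.

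**Conclusion.** The point holds as a minor wording error. As a signed inequality, the Grade 2 change band in SAP 7.6.8 selects nobody outside Grade 3. If it is programmed as written, falls of 10 to <20 points ending above 50% are tabulated as Grade 0 and left out of the LVEF abnormality count, so two participants with the same fall can be graded differently according to where they started.

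The consequence depends on literal coding, which the surrounding text makes unlikely. It also needs participants with a baseline above 60% and a fall of this size; their number is unknown and may be zero. Only the descriptive worst-grade table is exposed. The primary endpoint, sample size, other efficacy analyses and patient management are unaffected. The gap between 39% and 40% is a secondary matter that arises only if non-integer values are recorded.

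**What to change.** In SAP 7.6.8, write the Grade 2 change criterion as an absolute change from baseline ≤ -10 and > -20 percentage points, leaving the Grade 3 change criterion as it stands. If LVEF can be recorded as a non-integer, add a sentence saying how values between 39% and 40% are graded, either by closing the band or by stating a rounding rule; the documents do not favour one over the other.

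The cost is one line of tabulation text, with a second sentence if needed. No new data are required, and nothing changes in efficacy analysis or patient management.

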7.3.8. Echocardiogram/Multi-gated Acquisition

Cardiac ejection fraction will be assessed by transthoracic ECHO or MUGA at the time points specified in SoA (Table 3). The same method should be used throughout the study. Patients who develop signs/symptoms of CHF at any point during the study are required to have an evaluation of LVEF measurements by ECHO or MUGA and should be monitored per institutional guidelines.

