The normal range of Calcium will be used as normal range for Corrected Calcium.

The following summaries will be produced for the hematology and chemistry laboratory data (by laboratory parameter) including central and local laboratory:

- Shift tables using CTCAE grades to compare baseline to the worst post-baseline value for laboratory parameters with CTCAE grades. For the laboratory parameters like blood sodium where participants can be graded for decreased or increased values, the worst post-baseline CTCAE grade will be presented for decrease and increase separately (e.g. hyponatremia and hypernatremia).
- Shift tables using CTCAE grades to compare baseline to the worst post-baseline value for laboratory parameters with CTCAE grades showing participants with Grade ≤ 2 at baseline and worst post baseline Grade 3 or 4.
- Tables reporting the worst post-baseline CTCAE grades for laboratory parameters.
- Shift tables using low, normal, high (as well as low and high combined) classifications to compare baseline to the worst post-baseline value for laboratory parameters where CTCAE grades are not defined.

The following listing will be produced for the laboratory data for all laboratory parameters are defined:

- All laboratory test results will be presented in listings sorted by participant identifier, laboratory test, and date/time of collection with values flagged to show the corresponding CTCAE grades and the classifications relative to the laboratory

reference ranges. Values outside laboratory normal ranges will be flagged where appropriate.

Hepatic Toxicity

Hepatic toxicity will be assessed based on the following Liver Function Tests (LFTs): ALT, AST, ALP, TBL, and INR. Frequency counts and percentages of participants having a newly occurring value in the categories in Table 6 will be provided.

An evaluation of Drug-Induced Serious Hepatotoxicity (eDISH) plot will also be created by graphically displaying

- peak serum ALT(/ULN) vs peak total bilirubin (/ULN) including reference lines at ALT =3×ULN and total bilirubin =2×ULN.
- peak serum AST(/ULN) vs peak total bilirubin (/ULN) including reference lines at AST =3×ULN and total bilirubin =2×ULN.

In addition, a listing of all LFTs values for participants having a newly occurring value in the categories presented in Table 6 will be provided.

Table 6. Hepatic Toxicity Criteria

Parameter	Criterion
ALT	>3xULN; >5xULN; >8xULN;>10xULN;>20 ULN
AST	>3xULN; >5xULN; >8xULN >10xULN;>20 ULN

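### The LVEF table reports an unchanged entry value of exactly 50% as a Grade 2 abnormality, and it grades change across ECHO and MUGA with no check on the effect

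*SAP*

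**What the plan says.** SAP 7.6.8 grades LVEF by two routes, the absolute value and the change from baseline. The Grade 2 rule reads "Grade 2: LVEF between 40% and 50%, inclusive, or absolute change from baseline between -10% and < -20" (in percentage points). For Grade 3 the absolute band is "Grade 3: LVEF between 20% and 39%, inclusive", and a fall of at least 20 points also qualifies. Grade 4 is below 20%.

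The counting rule is: "Participants will be considered as having a LVEF abnormality if the worst post value is grade 2, 3 or 4". One output is planned: "A table reporting the worst post-baseline LVEF value using CTCAE grades will be produced". On method, the section says: "Different modalities to assess LVEF might be used for the same participant. The CTCAE grades will be provided regardless of the modality". SAP 7.1.1 takes the last valid pre-dose assessment as baseline and sets no condition on modality.

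Two protocol rules bear on this. Section 7.3.8 says: "The same method should be used throughout the study". Exclusion 9c in Section 5.2 bars "LVEF < 50% as determined by MUGA or ECHO", so a patient at exactly 50% is eligible.

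Other safety sections of the SAP do separate new findings from existing ones. For liver tests, Section 7.6.5 says: "Frequency counts and percentages of participants having a newly occurring value in the categories in Table 6 will be provided". Table 7 counts the absolute QTcF thresholds only when new. CTCAE-graded laboratory parameters get shift tables from baseline to worst grade.

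**The concern.** Changes on ECHO/MUGA are part of the secondary safety endpoint (Protocol Section 3, SAP 3.1), and left ventricular dysfunction is a named risk of the regimen in Protocol 2.1.4. A reader will take the LVEF table as a count of declines on treatment. Two features let it count something else.

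First, the absolute limb of Grade 2 ignores where the patient started, and its upper edge coincides with the lowest eligible baseline. Second, the change limbs subtract a baseline value that may come from the other imaging method. Part of the difference may then belong to the method and not to the heart. The SAP foresees such switches but plans neither a restriction, nor a flag, nor a sensitivity table. Few events are expected, so one or two misplaced entries are visible, particularly in the smaller column.

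**Working it through.** The documents give no expected LVEF abnormality rate for this table, no number of switchers and no between-method difference. There is no figure of the plan's own to reproduce. The check applies the rules literally and then shows what the unknown part depends on.

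**Step 1: the rules applied to test cases.** The Grade 2 change wording is not well formed; I read it as a fall of at least 10 and less than 20 points.

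| Baseline | Post-baseline | Grade | Route |
|---|---|---|---|
| 50 | 50 | 2 | absolute band, no change |
| 51 | 51 | 0 | none |
| 55 | 55 | 0 | none |
| 65 | 55 | 2 | change only |
| 70 | 60 | 2 | change only |
| 75 | 55 | 3 | change only |

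An unchanged value is therefore flagged at 50 and not at 51 or above. Values below 50 are ineligible at entry. The last three rows show that a between-method difference of 10 points yields Grade 2, and one of 20 points Grade 3, even with both values above 50%.

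**Step 2: size of the baseline part.** SAP 7.1 splits every table into treatment-naïve, previously treated and total columns. With the planned numbers as denominators, each unchanged 50% entrant adds:
- total: 1/107 = 0.9 percentage points;
- previously treated: 1/37 = 2.7 percentage points.

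For scale only, Protocol 2.1.4 reports ejection-fraction decreases in 7% of patients in the melanoma trial: 0.07 × 107 = 7.5 patients. The documents do not show that this figure was derived by the same rules.

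**Step 3: what the modality part depends on.** Assume that true LVEF is unchanged, baseline is 60% or more, and the measured difference for one scan is normal with mean shift δ and standard deviation σ. The chance of Grade 2 or worse is Φ((−10 − δ)/σ). Every δ and σ below is an assumption.
- δ = 0: 0.6% (σ = 4), 2.3% (σ = 5), 7.7% (σ = 7), 10.6% (σ = 8).
- δ = −5: 10.6% (σ = 4) to 23.8% (σ = 7).
- δ = −8: 30.9% (σ = 4) to 38.8% (σ = 7).

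If 10 participants switched, again an assumption, the δ = 0 case with σ from 5 to 8 gives 10 × 0.0228 = 0.2 to 10 × 0.1056 = 1.1 flags. Not all of these are due to the switch, because same-method repeats vary too. If same-method σ were also 5, the excess at δ = 0, σ = 5 would be 2.3% − 2.3% = 0.

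**Step 4: Grade 3.** The change route needs a fall of 20 points. With δ = 0, Φ(−20/5) = 0.00003 and Φ(−20/8) = 0.006. With the larger shift, δ = −8 and σ = 7, Φ(−12/7) is about 0.04, against 0.388 for Grade 2 or worse. The effect falls mainly on Grade 2.

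**The case against.** The strongest reply is that very little is at stake. ECHO/MUGA has one scheduled pre-dose time point, at screening (Protocol Table 3), so the eligibility scan is normally the baseline. With 9c in force, any later value below 50% is new by construction. Only entrants at exactly 50% are affected, and there may be none. This stands, and it sets the reach of the first part.

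A second reply is that the SAP attributes the grades to CTCAE v4.03, which cannot be checked from these documents. The inclusive 50% boundary therefore cannot be called a SAP error. This also stands. The point concerns the counting rule, which ignores the baseline grade, and not the boundary itself. The SAP also tabulates worst grades without a condition on baseline for temperature and for laboratory parameters, but laboratory data have shift tables alongside and LVEF does not.

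A third reply is that grading everything regardless of modality is the cautious choice for safety. Discarding cross-modality change grades would turn a fall from 75% to 55% into Grade 0, since 55% lies above every absolute band. This is right and shapes the remedy: the all-modality table should stay.

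A reader might go further and infer that the table will be filled with false Grade 2 and Grade 3 cardiac toxicity. The documents do not support that. The protocol asks for one method, the SAP says only that modalities might differ, and false Grade 3 entries would need a 20-point difference. The SAP calls the result an LVEF abnormality; adverse events, with the investigator's grading, are summarised separately in SAP 7.6.4.

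**Conclusion.** The point holds in a limited form. The baseline part follows from the text alone: an eligible patient with an unchanged 50% is reported as a Grade 2 abnormality. Its size is 0.9 points in 107, or 2.7 points in 37, per such patient, and the number of such patients is unknown. The modality part is also plain on the text, but its size cannot be stated. The ranges above rest on assumed shifts, standard deviations and switch counts, and show only that the effect could run from nothing to a few Grade 2 entries. Importance is low. No hypothesis test or decision rule uses this table, and ORR is untouched.

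**What to change.** In SAP 7.6.8:

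1. Count as abnormal only participants whose worst post-baseline grade exceeds their baseline grade, or add a baseline-by-worst shift table as for laboratory data. The shift table is preferable because it removes nothing. Under the counting rule, an entrant at 50% who fell to 40% (50 − 40 = 10 points) would be Grade 2 at both times and would not be counted.
2. Keep the all-modality table. Add a repeat in which change-based grades use only a baseline from the same modality and other values are graded on the absolute bands alone.
3. Footnote the number of participants with a modality change.
4. While the section is open, restate the Grade 2 change range so that its limits are unambiguous.

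The cost is a few sentences, one extra descriptive table (two if the shift table is chosen) and minor programming. Some change-based grades will not be assessable, but only in the repeat.
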